7.2. Dose Modifications

7.2.1. Start of a New Cycle

Toxicity and adverse will be classified according to NCI's Common Terminology Criteria for Adverse Events Version 4.0 (CTCAE). A copy of the CTCAE can be downloaded from the CTEP home page:

(http://ctep.cancer.gov/protocolDevelopment/electronic_applications/ctc.htm#ctc_40).

Assessment of clinical benefit will be performed by investigators at the end of cycle 1 and confirmed with bone marrow studies as per MDS, CMML or O-AML specific response criteria (Appendices I and II) done at the end of cycles #2, 4, and 6 (i.e., at 8, 16, and 24 weeks, each +/- 7 days) and at the discretion of the physician thereafter.

A new treatment cycle will only be initiated when all of the following conditions are met:

- non- hematologic treatment related toxicities have improved to \leq Grade 1 (CTCAE v.4.0) or to the patient's baseline values (except alopecia)
- Platelets per 7.1 (platelets $> 10 \times 10^9/L$)

If blood counts are below this threshold at the 4 week point, blood work is to be repeated weekly until counts are at an acceptable level. Treatment will be restarted with appropriate dose modifications provided CTCAE hematologic grade ≥ 4 is not prolonged for more than 6 weeks in the absence of persistent disease. If treatment is unable to restart within 4 weeks of the planned treatment date, the patient will be permanently discontinued from study therapy.

CTCAE v.4.0 Adverse Effects Terms & Descriptions (see below for allergic reaction/hypersensitivity)	765IGF-MTX Dose Modifications (for treatment-related toxicities deemed clinically significant)
Any persistent (>4 weeks) grade 2 treatment-related non-hematologic toxicity	Drop to next lower dose level or discontinue treatment.
Grade 4 or greater treatment-related hematological toxicity for >7 days.	Drop to next lower dose level or discontinue treatment.
Grade 3 or greater treatment-related clinical non-hematological toxicity, excluding grade 3 nausea, vomiting, or diarrhea without maximal medical intervention and/or prophylaxis.	Drop to next lower dose level or discontinue treatment.
Febrile neutropenia.	Drop to next lower dose level or discontinue treatment.
Platelets less than $10 \times 10^9/L$	Wait to improve and then drop to next lower dose level or discontinue treatment.

CTCAE Grade 1 Allergic Reaction/Hypersensitivity: (Transient flushing or rash, drug fever $< 38^{\circ}C$): Supervise without further treatment for allergic reaction/hypersensitivity.

CTCAE Grade 2 Allergic Reaction/Hypersensitivity: (Rash, flushing, dyspnea, urticaria, drug fever greater than or equal to $38^{\circ}C$) and/or asymptomatic bronchospasm: Interrupt the infusion. If symptoms abate, attempt re-infusion at a slower rate. If the symptoms recur,

discontinue infusion and follow for recurrent allergic reaction/hypersensitivity in the next paragraph.

Recurrent CTCAE Grade 2 or CTCAE Grade 3 or 4 Allergic Reaction/Hypersensitivity:

Stop the infusion. Administer additional doses of H1 and H2 blockers intravenously. Administer IV steroids and consider epinephrine and bronchodilators as clinically indicated.

CTCAE Grade 3 or 4 Allergic Reaction/Hypersensitivity: Stop the infusion. Administer additional doses of H1 and H2 blockers intravenously. Administer IV steroids and consider epinephrine and bronchodilators as clinically indicated. Will be permanently discontinued from study treatment.

Prior to re-challenge of Grade 2 allergic reaction/HSR and with all subsequent cycles:

The following prophylactic premedications are recommended for future infusions: give both an H1 and H2 blocker intravenously plus dexamethasone 20 mg (orally or intravenously) within 30 to 60 minutes before 765IGF-MTX infusion. Dexamethasone could be used at the investigator's discretion in subsequent cycles for recurrent (i.e. occurring despite slowing infusion as discussed above) Grade 2 reactions but would not be mandated.

An appropriate resuscitation plan should be in place and a physician readily available during the period of drug administration. If treatment delay necessitates a period longer than 4 weeks, treatment is stopped and the subject is discontinued from the study.

7.3. Permitted Concomitant Medications and Procedures

Myeloid growth factors to treat patients with neutropenia or cytopenia are permitted.

Antiemetic agents may be administered at the discretion of the investigator but are not commonly required as a prophylactic agent. All other manifestations of the patient's malignancy should be treated at the discretion of the investigator.

Medications with potential CNS effects are not prohibited in this study, but it is recommended that their use be minimized to avoid confusion in the interpretation of CNS effects should they occur during the course of treatment with 765IGF-MTX.

In appropriate settings, such as combinations with agents known to produce frequent thrombocytopenia, restricted uses of anticoagulants should be considered.

All other medical conditions should be treated at the discretion of the investigator in accordance with local community standards of medical care.

7.4. The Effects of Other Drugs on Methotrexate

Nonsteroidal anti-inflammatory drugs should not be administered prior to or concomitantly with the high doses of methotrexate, such as used in the treatment of osteosarcoma.

Concomitant administration of some NSAIDs with high dose methotrexate therapy has been reported to elevate and prolong serum methotrexate levels, resulting in deaths from severe hematologic and gastrointestinal toxicity.

Caution should be used when salicylates are administered concomitantly with lower doses of methotrexate. These drugs have been reported to reduce the tubular secretion of methotrexate in an animal model and may enhance its toxicity.

Methotrexate is partially bound to serum albumin, and toxicity may be increased because of displacement by certain drugs, such as salicylates, phenylbutazone, phenytoin, and sulfonamides including BACTRIM. Renal tubular transport is also diminished by probenecid; use of methotrexate with this drug should be carefully monitored.

Methotrexate increases the plasma levels of mercaptopurine. The combination of methotrexate and mercaptopurine may therefore require dose adjustment.

Oral antibiotics such as tetracycline, chloramphenicol, and nonabsorbable broad spectrum antibiotics, may decrease intestinal absorption of methotrexate or interfere with the enterohepatic circulation by inhibiting bowel flora and suppressing metabolism of the drug by bacteria.

Penicillins may reduce the renal clearance of methotrexate; increased serum concentrations of methotrexate with concomitant hematologic and gastrointestinal toxicity have been observed with high and low dose methotrexate. Use of methotrexate with penicillins should be carefully monitored.

The potential for increased hepatotoxicity when methotrexate is administered with other hepatotoxic agents has not been evaluated. However, hepatotoxicity has been reported in such cases. Therefore, patients receiving concomitant therapy with methotrexate and other potential hepatotoxins (e.g., azathioprine, retinoids, sulfasalazine) should be closely monitored for possible increased risk of hepatotoxicity.

Methotrexate may decrease the clearance of theophylline; theophylline levels should be monitored when used concurrently with methotrexate.

Vitamin preparations containing folic acid or its derivatives may decrease responses to systemically administered methotrexate.

Folate deficiency states may increase methotrexate toxicity. Trimethoprim/sulfamethoxazole has been reported rarely to increase bone marrow suppression in patients receiving methotrexate, probably by decreased tubular secretion and/or an additive antifolate effect.

7.5. Concomitant Medications and Non-Drug Therapies

All patients will be asked to provide a complete list of prescription and over-the-counter medications that have been taken within the 4 weeks prior to screening. The investigator must be informed as soon as possible about any new medication(s) taken from the time of screening until the completion of the post-treatment follow-up visit.

7.6. Prohibited Concomitant Medications and Concomitant Medications to be used with caution.

The only prohibited concomitant medications are mercaptopurine, and concomitant other anti-cancer therapy (cytotoxic, biologic, or radiation).

Concomitant use of salicylates, sulfonamides, BACTRIM (trimethoprim/sulfamethoxazole) and phenylbutazone is not prohibited, but should be used with caution because of their interactions with high dose methotrexate (doses greater than or equal to 500mg/m² of methotrexate are considered high), although the methotrexate doses used in this study are not high (the highest dose of 765IGF-MTX used in this study of 2.5 microEq/kg is about equal to 45 mg of methotrexate per meter²).

Patients should not receive other anti-cancer therapy (cytotoxic, biologic, or radiation) while on treatment in this study.

7.7. Management of Clinical Events and Supportive Care Guidelines

Optimal patient care is to be provided to all patients.

Patients should receive full supportive care during the study, including transfusion of blood and blood products, treatment with antibiotics, analgesics, or erythropoietin, when appropriate.

Although acetaminophen at doses of ≤ 2 grams/day is permitted, it should be used with caution in patients with impaired liver function.

Patients with significant third spacing (anasarca, symptomatic pleural effusions, symptomatic ascites) should be monitored closely.

Infusion of IGF-methotrexate for 1.5 hours and follow up observation for an additional 1-2 hours (see section 7.1.1. for further details on duration of follow up observation) will be performed in monitored room with available sealed cart with Diazepam 2 mg vials for immediate intravenous infusion in case of seizures. The following protocol will be in place in case of this drug toxicity:

- Call physician on service.
- Start BLS SPECIFIC CARE:
 - Administer oxygen (high flow if neurological deficits or altered mental status)
 - Place the patient in recovery position, and prevent accidental harm.
 - Anticipate brief combativeness or agitation in post-ictal phase.
- Start ALS SPECIFIC CARE:
 - Anticonvulsant Therapy
 - Diazepam (Valium): IV: 2-10 mg, every 5-10 minutes as needed (max of 20 mg), if status epilepticus start phenytoin load 20 mg/kg.

Once the situation is resolved, the duration of further monitoring will be at the discretion of the study physician.

7.8. Nausea and Vomiting

Prophylactic antiemetic therapy will not be used in this study unless it becomes clear that 765IGF-MTX causes acute nausea and vomiting. If prophylactic antiemetic therapy is needed, 5-HT₃ receptor antagonists (without corticosteroids) should be tried first. Because of the potential of benzodiazepines to cause sedation, the use of benzodiazepines for antiemetic prophylaxis should be reserved for patients who cannot be satisfactorily managed otherwise.

Although this study will not initially employ prophylactic antiemetics, there is no prohibition against antiemetic use in the management of a patient who develops nausea or vomiting, or both.

7.9. Diarrhea

Antidiarrheal medications will not be used prophylactically; however, patients will be instructed to take loperamide, 4 mg, at the occurrence of the first loose stool and then 2 mg

every 2 hours until they are diarrhea-free for at least 12 hours. During the night, patients may take 4 mg of loperamide every 4 hours. Fluid intake should be maintained to avoid dehydration.

7.10. Duration of Therapy

Patients will receive protocol therapy unless:

- Extraordinary Medical Circumstances: If at any time the constraints of this protocol are detrimental to the patient's health, protocol treatment should be discontinued.
- Patient withdraws consent.
- There is evidence of progressive disease or unacceptable toxicity.
- The treating physician thinks a change of therapy would be in the best interest of the patient.
- More than a 4 week delay between cycles

7.11. Follow-up

Administration of study medication will be continued after cycle 2 until disease progression, unacceptable toxicity, or patient withdrawal. A final study visit will occur 30 days (+/-1 week) after the last dose of 765IGF-MTX. This visit will end study participation unless there is ongoing toxicity at least possibly related to study treatment. In this case, the patient will be followed as medically appropriate until resolution or stabilization of the adverse event.

8. Study Parameters

8.1. Standard of Care Procedures

	Baseline, within 28 days of enrollment	Each treatment cycle ^a			Every 8 weeks (± 1 week)	30 days (± 1 week) after final dose of 765IGF-MTX ¹
		Day 1 ² (±1 day)	Day 8 (±1 day)	Day 15 (±1 day)		
Signed consent (Registration/ Enrollment must occur within 30 days.)	X					
Medical history	X	X				X
Review of prior therapy	X					
Bone marrow biopsy and aspirate confirming disease and blast count ³	X				X ³	
Physical exam	X	X				X
Vital signs	X	X	X	X		X
Height, weight	X	X				X
Concomitant meds review	X	X	X	X		X
Performance status	X	X				X
Symptom and toxicity	X	X	X	X		X ³
CBC w/ diff	X	X	X	X		X
CMP (with: calcium, glucose, sodium, potassium, CO ₂ , chloride, BUN, creatinine, albumin, ALT, AST, bilirubin, alkaline phosphatase, total protein)	X	X	X	X		X
Uric acid (cycle 1 only)	X	X		X		
LDH	X	X				
HbA1C for diabetic patients	X					X
Serum pregnancy test for females of child- bearing potential	X					
ECG ⁴	X	X				X
765IGF-MTX administration			X	X		

^a Subsequent cycles beyond cycle 1 must meet the criteria found in section 7.3 and may begin 1 day earlier or up to 2 days later to accommodate scheduling issues.

¹ For patients who leave treatment with a response, repeat appropriate disease assessment every 6-12 weeks until progression or start of a new treatment.

² For cycle 1 only, tests and procedures do not need to be repeated if done within 3 days of day 1.

³ Bone marrow biopsy should be at end of end of cycle 2, and every 2 cycles thereafter to cycle 6. Patients who achieve response (CR) could have repeat bone marrow biopsies per MD discretion.

⁴ ECG performed at screening, at cycle 1 and at the end of study visit 30 days after the final dose.

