2.2. Secondary Objectives

2.2.1 Evaluate clinical benefit of 765IGF-MTX by evaluating the overall response rate (ORR) complete and partial remission (CR and PR) rates, complete remission with incomplete hematologic recovery (CRi) rate, relapse-free survival (RFS), cumulative incidence of relapse (CIR), time to relapse, and overall survival (OS) in patients with advanced, previously treated O-AML, CMML or MDS.

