6.2. Registered/Enrolled Patients Who Do Not Begin Study Treatment

If a patient signs the informed consent document, is subsequently registered/enrolled to the study but is then not able to begin the planned study treatment for any reason, the patient will be removed from study and treated at the physician's discretion. The patient will be considered a screen/baseline failure and be replaced. Further data will not be collected if the patient has not begun study treatment at the time of removal from trial. The reason for removal from study will be clearly indicated in EDC Easy®.

If a patient begins treatment and is then removed from treatment for any reason, the patient must be followed per section 7.11.

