Relapse-free survival*	Defined only for patients achieving CR or CRI;‡ measured from the date of achievement of a remission until the date of relapse or death from any cause; patients not known to have relapsed or died at last follow-up are censored on the date they were last examined
Event-free survival	Defined for all patients of a trial; measured from the date of entry into a study to the date of induction treatment failure, or relapse from CR or CRI;‡ or death from any cause; patients not known to have any of these events are censored on the date they were last examined
Cumulative incidence of relapse (CIR)†	Defined for all patients achieving CR or CRI;‡ measured from the date of achievement of a remission until the date of relapse; patients not known to have relapsed are censored on the date they were last examined; patients who died without relapse are counted as a competing cause of failure

*Relapse-free and disease-free survival have been used with the same definition

†It is important to provide estimates of cumulative incidence of death (CID) as well, since just considering the results of CIR may be misleading if for instance CIR is lower for one group but CID is actually higher for that same group.

‡In studies where the criterion CRI is used, relapse-free survival should be defined for all patients achieving CR or CRI; for event-free survival, relapse should be considered from CR and CRI.

FAILURE - aplasia Aplasia: Patient survives \geq 7 days following completion of initial treatment course then dies while cytopenic, with the last post-induction bone marrow aplastic or hypoplastic (i.e. < 20% cellularity) and without leukemia blasts.

FAILURE - indeterminate Indeterminate: (a) Patient survives < 7 days after completion of initial treatment course; **or** (b) patient survives \geq 7 days following completion of initial treatment course then dies with no persistent leukemia in the peripheral smear but no post-induction bone marrow examination.

RELAPSE FROM CR Relapse: Reappearance of leukemia blasts in the peripheral blood; or > 5% blasts in the bone marrow not attributable to another cause (e.g., recovery of normal cells following chemotherapy-induced aplasia); or appearance or reappearance of extramedullary disease.

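### Section 7.11 ends participation about 30 days after the last dose, before any off-treatment disease assessment that Table 8.1 footnote 1 requires, so relapse follow-up of responders who stop without relapse is undefined

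*Combined protocol and SAP*

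**What the plan says.** Section 2.2 lists "relapse-free survival (RFS), cumulative incidence of relapse (CIR), time to relapse" among the secondary objectives. Section 3.2 repeats relapse-free survival (RFS) and cumulative incidence of relapse (CIR) as endpoints, and 13.4.1 plans a descriptive analysis of both.

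Two passages govern what happens after treatment stops.

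- Table 8.1, footnote 1, attached to the 30-day column: patients who stop treatment while in response are to "repeat appropriate disease assessment every 6-12 weeks until progression", or until a new treatment begins.
- Section 7.11: "A final study visit will occur 30 days (+/-1 week) after the last dose of 765IGF-MTX". It continues: "This visit will end study participation unless there is ongoing toxicity at least possibly related to study treatment". The follow-up allowed under that exception is of the adverse event, not of the disease.

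Section 6.2 says that, for a patient who begins treatment and is then taken off it for any reason, "the patient must be followed per section 7.11". It does not mention the footnote. Section 12.2 has the record updated until death or the end of required participation, without saying which rule sets that end.

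Appendix I (Table 6) defines RFS for patients in CR or CRi, "measured from the date of achievement of a remission until the date of relapse or death from any cause". For both RFS and CIR, a patient without a recorded event is censored at the last examination.

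**The concern.** A responder who stops treatment without relapsing falls under two rules with different end dates. Because Appendix I censors at the last examination, the rule that is followed sets the censoring date. Under footnote 1, disease follow-up runs until progression or new treatment. Under 7.11 it stops about a month after the last dose, and a remission that outlasts that visit contributes nothing further.

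The protocol allows treatment to stop without relapse: 7.10 lists unacceptable toxicity, withdrawal of consent, the physician's judgement and a delay of more than 4 weeks between cycles. Responders are likely to be few, so each censoring date carries weight. Section 11.4 refers to principal investigators at two institutions, so the passages could be read differently in different places.

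**Working it through.** The plan states no figure on this point to reproduce: 13.1 fixes no sample size and bases none on hypothesis testing. The check is calendar arithmetic from the protocol's own schedule, followed by one illustration that rests on assumptions.

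**Inputs from the documents**

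- Doses on days 1, 8 and 15 of a 28-day cycle (section 4, 7.1.1).
- Marrow at the end of cycles 2, 4 and 6 (7.2.1, Table 8.1 footnote 3).
- Final visit 30 ± 7 days after the last dose (7.11).
- Footnote 1 interval of 6 to 12 weeks, that is 42 to 84 days.

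**Step 1: do the two rules overlap?**

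Exit under 7.11: 30 − 7 = 23 to 30 + 7 = 37 days after the last dose. The first footnote assessment is 42 to 84 days after the last dose, and later if counted from the final visit. Since 37 < 42, no footnote assessment falls within participation. Table 8.1 schedules blood counts and clinical review at the 30-day visit, but no marrow.

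**Step 2: follow-up from remission under 7.11**

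Take a response documented at the nominal end of cycle c, in a patient whose last dose was day 15 of that cycle.

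- Last dose: study day 28(c − 1) + 15
- Marrow: study day 28c
- Exit: last dose + 23 to last dose + 37

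| c | Last dose | Marrow | Exit | Exit minus marrow | First footnote assessment (from last dose) |
|---|---|---|---|---|---|
| 2 | 43 | 56 | 66–80 | 10–24 days | 85–127 |
| 4 | 99 | 112 | 122–136 | 10–24 days | 141–183 |
| 6 | 155 | 168 | 178–192 | 10–24 days | 197–239 |

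At the nominal 30-day visit the follow-up is 17 days (for c = 2, 73 − 56). Appendix II requires an MDS response to last at least 4 weeks. From a day-56 marrow that is day 84, after the latest exit on day 80. These figures use the nominal marrow date, and an earlier or later marrow shifts them by the same number of days. A patient whose remission was documented in an earlier cycle has longer follow-up from remission, but still only 23 to 37 days after the last dose.

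**Step 3: illustration only**

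The documents give no relapse rate. Assume exponential relapse after stopping, with median m months (30.44 days per month):

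P(relapse by day d) = 1 − 2^(−d / (30.44 m))

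| Assumed median | By day 30 | By day 37 | After day 30 | After day 37 |
|---|---|---|---|---|
| 3 months | 20.4% | 24.5% | 79.6% | 75.5% |
| 6 months | 10.8% | 13.1% | 89.2% | 86.9% |
| 12 months | 5.5% | 6.8% | 94.5% | 93.2% |

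Across these cases, about 76% to 94% of relapses in responders who stopped without relapse would come after the exit visit.

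**The case against.** Four points can be made for the plan.

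1. *The footnote describes routine care.* It sits in a table of standard-of-care procedures, so the visits could take place after formal participation ends. This reading is possible, but nothing in the protocol says that such data would be collected or analysed, and 12.2 stops updating the record at the end of required participation.
2. *A full SAP is promised before database lock (section 13).* It can set censoring rules. It cannot recover assessments that were never made or recorded.
3. *The endpoints are secondary and descriptive, in a dose-finding pilot.* This stands. No error rate, sample size or dose decision depends on the conflict.
4. *Few patients are affected.* This also stands. Treatment continues until progression, so relapses on treatment are captured under either rule.

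A reader might infer three stronger claims that the documents do not support.

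- *That the conflict touches everyone on whom RFS and CIR are defined.* Appendix I defines them for all patients in CR or CRi, including those who relapse on treatment; only those who stop without relapse are affected.
- *That 76% to 94% of all relapses in the trial would be lost.* The figure applies only to relapses after stopping in that subset, under assumed medians. The documents give neither a median nor the size of the subset.
- *That the 6-to-12-week range is itself an error needing one fixed interval.* Marrow is discretionary after CR (footnote 3) and after cycle 6 (section 4, 7.2.1), so fixing the off-treatment interval would not put all patients on one grid. Blood findings can also reveal relapse between visits under both appendices.

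**Conclusion.** The contradiction is real and limited. Section 7.11, reinforced by 6.2, closes participation before the first assessment that footnote 1 requires, and no passage says which rule governs. The affected patients are responders who stop treatment without relapse.

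If 7.11 is followed, their RFS, CIR and time to relapse are cut off about 30 days after the last dose. In the short case worked above, this leaves 10 to 24 days from documented remission. That result needs only the protocol's nominal schedule. The cut-off for RFS and CIR follows from Appendix I's last-examination rule, which is written for acute leukaemia; Appendix II gives no censoring rule of its own. The 76% to 94% depends on the exponential form and the assumed 3-to-12-month medians, and is an illustration.

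This should be corrected, because the missing data cannot be recovered later. It does not threaten the primary objective.

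**What to change.** Add a second exception to 7.11: patients who leave treatment in response remain on study for outcome data collection as in Table 8.1 footnote 1, until relapse or progression or the start of a new treatment. State that these assessments are entered in the study database and used for RFS, CIR and time to relapse. Define the group by the appendices: CR or CRi for RFS and CIR under Appendix I, and CR or PR for the relapse definition in Appendix II. The pointer in 6.2 and the record-keeping rule in 12.2 then work without further change. The 6-to-12-week interval can stay.

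The cost is a protocol wording change and a few more data-collection visits, which footnote 1 already requests, in a small number of patients.
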